14.3.7 Summary of change from baseline for vital signs (Safety set)

Lambda Therapeutic Research Ltd.

Confidential

Project No. 0110-23

Table 14.3.7

Parameters	TT: '. (D.)	m:		TRTR	RTRT	Total
(Unit)	Visit (Day)	Time Point	Statistics	(N=xx)	(N=xx)	(N=xx)
Diastolic Blood Pressure (mmHg)	Assessment Visit X	Time Point 1	n	xx	xx	xx
			Mean (SD)	xx.x (xx.xx)	xx.x (xx.xx)	xx.x (xx.xx)
			Median	xx.x	XX.X	XX.X
			Min, Max	XX.X, XX.X	XX.X, XX.X	XX.X, XX.X
		Time Point 2	n	XX	XX	xx
			Mean (SD)	xx.x (xx.xx)	xx.x (xx.xx)	xx.x (xx.xx)
			Median	XX.X	XX.X	XX.X
			Min, Max	xx.x, xx.x	XX.X, XX.X	xx.x, xx.x
	Assessment Visit Y	Time Point 1	n	xx	xx	xx
			Mean (SD)	xx.x (xx.xx)	xx.x (xx.xx)	xx.x (xx.xx)
			Median	XX.X	XX.X	XX.X
			Min, Max	xx.x, xx.x	xx.x, xx.x	XX.X, XX.X
Etc.	Etc.	Etc.				

N = Number of subjects in safety set, n = Number of subjects in respective categories Change from Baseline (CFB) = Post Baseline assessment - Baseline assessment (0.00 Hrs Pre-Dose). Treatment specification -> T = Test Product and R = Reference Product. Reference Listing: 16.2.9.4

Project No. 0110-23

Lambda Therapeutic Research Ltd. Statistical Analysis Plan (SAP) Albendazole Tablets IP 400 mg

14.3.8 Summary of quantitative safety laboratory variables (Safety set)

Lambda Therapeutic Research Ltd.

Confidential

Table 14.3.8

Summary of quantitative safety laboratory variables (Safety set)

Parameters	Visit	Statistics	TRTR	RTRT	Total
(Unit)	vioit Statistics		(N=xx)	(N=xx)	(N=xx)
Hemoglobin (g/dL)	Screening	n	XX	XX	xx
		Mean (SD)	xx.x (xx.xx)	xx.x (xx.xx)	xx.x (xx.xx)
		Median	xx.x	xx.x	xx.x
		Min, Max	xx.x, xx.x	xx.x, xx.x	xx.x, xx.x
	Assessment Visit X	n	xx	xx	xx
		Mean (SD)	xx.x (xx.xx)	xx.x (xx.xx)	xx.x (xx.xx)
		Median	xx.x	xx.x	XX.X
		Min, Max	xx.x, xx.x	xx.x, xx.x	xx.x, xx.x
	Assessment Visit Y	n	xx	xx	xx
		Mean (SD)	xx.x (xx.xx)	xx.x (xx.xx)	xx.x (xx.xx)
		Median	XX.X	XX.X	XX.X
		Min, Max	xx.x, xx.x	xx.x, xx.x	xx.x, xx.x
Etc.	Etc.				

N = Number of subjects in safety set, n = Number of subjects in respective categories

Treatment specification \rightarrow T = Test Product and R = Reference Product.

Quantitative data values observed out of limit of quantification are adjusted to quantification limits for descriptive statistics. In case of repeat sample collection latest result has been considered for the analysis.

Reference Listings: 16.2.8.1

Output Generated on: DDMMMYYYY hh:mm

<Note to Programmer: This table will continue for all other Laboratory parameters and some additional test.>

Project No. 0110-23

Lambda Therapeutic Research Ltd. **Statistical Analysis Plan (SAP)** Albendazole Tablets IP 400 mg

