2.3. Benefit/risk assessment

Participation in bioavailability studies yields no direct benefit to the participants. However, a charge-free study related health assessment is provided. The risks as described below are reduced considering the fact only 4 doses are to be administered at an interval of at least 7 days between dosing days of any 2 successive periods.

Table 3 Potential risks and risk mitigation strategies

The potential risks of clinical significance for albendazole tablets are derived from the prescribing information (Albendazole label). Most of these reported risks are uncommon, rare or very rare. The likelihood of these risks in a healthy population receiving a single dose is therefore expected to be low. For complete list of adverse reactions please refer the prescribing information mentioned above.

Potential Risk of Clinical Significance	Summary of Data/Rationale for Risk	Mitigation Strategy
	Study Intervention(s)	
Hepatotoxicity	In 2001, GSK routine monitoring of spontaneous ADRs identified an increased number of reports of elevated liver enzymes in patients receiving low dose albendazole and reports of hepatitis and jaundice in patients receiving high dose albendazole. Higher doses of albendazole are used to treat systemic helminth infections for longer periods compared to the low dose, short treatment durations required for intestinal helminth infections in the OTC environment. A cumulative review of hepatic events was conducted to further evaluate the nature of these events and to determine whether GSK's CSI adequately reflected these adverse events. Following the review of the available data, GSK concluded that there was sufficient evidence to suspect albendazole as causing hepatic events; with low dose albendazole causing	This study will not include participants with abnormal liver function test results (transaminases). Discontinuation of study intervention in the best interest of the participant for abnormal liver tests at the investigator discretion, when liver parameter falls outside the pre-defined clinically acceptable values. If any participant has clinically significant abnormal liver function analysis during the study, in such case participant may be discontinued for specific period at the investigator discretion. The decision to continue/discontinue such participants will be based on investigator's decision.

Protocol Version No. 1.0

Detential Diely of Clinian	Summaria of	Mitigation Stratogy		

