8.3.4. Clinical safety laboratory tests

- See Section 10.2 for the list of clinical laboratory tests to be performed and the SoA (Section 1.3).
- Serology tests (HIV AB (1 & 2), Anti HCV and HBsAg) will be performed at the time of screening.
- Urine parameters will be performed at the time of screening.
- Laboratory assessment for hematology and biochemistry will be performed at the time of screening.
- Laboratory assessment for hematology and biochemistry (except random glucose, sodium, potassium, chloride, alkaline phosphatase) will be performed at the end of the study (at the time of check-out of period IV).
- Laboratory assessment for liver function test (SGPT, SGOP and total bilirubin) will be performed prior to check-in of period II, III and IV.
- The investigator must review the laboratory results, document this review, and record any clinically significant changes occurring during the study as an AE. The laboratory results must be retained with source documents.
- All laboratory tests with values considered clinically significantly abnormal during participation in the study should be repeated until the values return to normal or baseline or are no longer considered clinically significant by the investigator or medical monitor.
 - o In the absence of a diagnosis, abnormal laboratory findings assessments or other abnormal results the investigator considers clinically significant will be recorded as an AE or SAE, if they meet the definition of an AE or SAE (refer to Section 10.3.1 and Section 10.3.2).
 - o If clinically significant values do not return to normal/baseline within a period of time judged reasonable by the investigator, the etiology should be identified, and the sponsor notified.
 - o If laboratory values from non-protocol-specified laboratory tests performed at the institution's local laboratory require a change in participant management or are considered clinically significant by the investigator (e.g, SAE or AE), then the results must be recorded.

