7.2 Safety Analysis

Safety analysis will be done on the safety set. Safety variables include AEs, clinical laboratory parameters, vital signs, physical examinations. Safety variables will be listed and summarized with descriptive statistics as appropriate.

Continuous variables will be Summarized by treatment/sequence group using summary statistics (number of observations, mean, standard deviation, median, minimum and maximum etc.) as applicable. Categorical values will be summarized by the treatment group using frequencies and percentages.

Result obtained when evaluating safety (adverse events, vital signs, clinical laboratory tests etc.) will be listed and evaluated descriptively.

Adverse events

All AEs reported during the study must be included in the safety analysis. AEs will be classified by system organ class, by preferred term from the MedDRA version 25.0 or higher. They will be presented in individual listings and summary tables, and evaluated descriptively and in terms of

frequencies, by treatment. As will be summarized for all subjects in Safety set across two treatment groups by System Organ Class (SOC) and Preferred Term (PT). p-value using chi-square test or fisher exact test will be provided for the AE data.

Intensity refers to the severity of the AE.: Mild, Moderate, Severe.

Clinical laboratory values

LAMBDA

Clinical laboratory values will be compared to their reference ranges. Values outside the normal ranges will be highlighted. The Investigator has to comment, whether the abnormality is clinically relevant.

Other safety parameters

All results of vital sign measurements will be presented in individual listings. Where appropriate, results and possible changes in parameters will be evaluated descriptively or by descriptive statistics (mean, SD, median, range). Descriptive statistics (N, n, mean, SD, median, minimum and maximum) will be presented for absolute and change from baseline values of vital signs parameters at each timepoint.

Demographic data will be shown in tables as mean values, SD and ranges (min, max).

Clinical laboratory data will be shown in tables as mean values, SD and ranges (min, max) as applicable.

Physical examination, 12 lead ECG, Chest X-Ray performance and concomitant medication will be presented in data listings.

Protocol deviations

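### As worded, the latest-result rule in SAP Table 14.3.8 can replace an abnormal post-dose laboratory value with a later, less abnormal repeat

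*SAP*

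**What the plan says.** **The summary rule.** The footnote to SAP shell 14.3.8 (quantitative laboratory variables, Safety set) states: "In case of repeat sample collection latest result has been considered for the analysis". Shell 14.3.9 (qualitative variables) carries the same sentence. Neither says what counts as a repeat, or how a follow-up sample is assigned to a visit.

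**The repeat rule.** Protocol 8.3.4 says that clinically significantly abnormal results obtained during participation "should be repeated until the values return to normal or baseline or are no longer considered clinically significant by the investigator or medical monitor".

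**The tests concerned.** The same section states: "Laboratory assessment for liver function test (SGPT, SGOP and total bilirubin) will be performed prior to check-in of period II, III and IV". Protocol Table 12 also has total bilirubin, AST and ALT in the end-of-study panel. The reason is in Protocol 2.3, Table 3, where hepatotoxicity is the first risk. It cites "reports of elevated liver enzymes in patients receiving low dose albendazole" and concludes that "there was sufficient evidence to suspect albendazole as causing hepatic events".

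**The planned laboratory output.** SAP 7.2: "Clinical laboratory data will be shown in tables as mean values, SD and ranges (min, max) as applicable". Shell 14.3.8 gives n, mean (SD), median, minimum and maximum by visit, in columns for TRTR, RTRT and total. The SAP's list of tables has no shift table, worst-value table or count outside limits.

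**Other routes into the report.** Protocol 8.3.4 also tells the investigator to "record any clinically significant changes occurring during the study as an AE". SAP 7.2 has out-of-range values highlighted, and Listing 16.2.8.1 shows each result with its date, time and flag.

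**The concern.** Each rule is unremarkable alone. Together they make the tabulated value depend on the result. An unremarkable value is not repeated and stays in the table. A clinically significant one is repeated, and a series followed to its end stops at a value that is less abnormal or no longer judged significant. If that last value is the one analysed, the substitution runs in one direction only, toward normal.

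The post-dose liver tests are the case that matters. The protocol schedules them against a named risk, and a rise in one or two participants would show in a by-visit summary mainly through the maximum. That is the statistic most exposed to the rule. At stake is whether the one quantitative laboratory table conveys how large an enzyme rise was.

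**Working it through.** The documents state no figure to reproduce. The check is a comparison of rules followed by an illustration.

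**Step 1. Follow one abnormal value through the rules.**

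| Stage | Source | Result |
|---|---|---|
| Scheduled post-dose liver test is clinically significantly abnormal | Protocol 8.3.4 | Must be repeated and recorded as an adverse event |
| Repeats stop at normal, at baseline, or when no longer clinically significant | Protocol 8.3.4 | Last value is typically less abnormal than the first, though possibly still out of range |
| Latest result is analysed when a sample is repeated | SAP 14.3.8 footnote | Last value enters mean, SD, median, minimum and maximum |
| Event is summarised | SAP Tables 14.3.1 to 14.3.4 | Counted as an event by product, severity and relationship, without its numerical size |
| Individual result is listed | SAP Listing 16.2.8.1 | First value should be shown with its flag |

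The count n does not change; the value behind it does.

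**Step 2. Look for another summary of size.** The list of tables contains none. The maximum in 14.3.8 is the only summary entry in which a single excursion would be visible as a number.

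**Step 3. Illustrate the effect.** From the documents: 70 participants planned with equal allocation (Protocol 9.6 and 6.3), so 70/2 = 35 per sequence column; upper acceptable ALT for men 82 U/L (Protocol 10.6). Assumed: the other 34 participants have ALT mean 25 and SD 8 U/L, with a highest value of 42 in the simulated set used; one man has first value x and last repeat 40 U/L.

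- Mean = (34 × 25 + x)/35
- SD = √{[33 × 8² + (34/35)(x − 25)²]/34}

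Latest-result rule, x = 40: mean = 890/35 = 25.4; SD = √[(2112 + 218.6)/34] = 8.3; maximum 42. This row is the same whatever the first value was.

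First scheduled value kept:

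| First ALT (U/L) | Mean | SD | Maximum | Mean shift, (x − 40)/35 |
|---|---|---|---|---|
| 100 | 27.1 | 14.9 | 100 | 1.7 |
| 164 (2 × 82) | 29.0 | 24.8 | 164 | 3.5 |
| 246 (3 × 82) | 31.3 | 38.2 | 246 | 5.9 |
| 410 (5 × 82) | 36.0 | 65.6 | 410 | 10.6 |

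**Step 4. Vary the denominator.** For x = 246 the difference is 206 U/L. Over all 70 participants the mean shift is 206/70 = 2.9 U/L. If only the 48 completers assumed in Protocol 9.6 remain, 24 per sequence, it is 206/24 = 8.6 U/L. The change in the maximum, 246 to 42, does not depend on the denominator.

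**The case against.** The strongest reply is that the report does not lose the event. The finding that triggers a repeat under Protocol 8.3.4, clinical significance, is also what makes the change an adverse event. It should therefore reach SAP Tables 14.3.1 to 14.3.4 by product, and the first value should stand, flagged, in Listing 16.2.8.1. That is right. A reader might infer that an abnormal liver value would vanish from the report, or that the report would show no liver signal when there was one. The documents do not support either inference. What remains is narrower: the adverse event tables carry no magnitude, and a clean range in 14.3.8 gives no cue to search the listings.

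Second, the SAP does not define a repeat. Protocol 8.5 provides extra blood for haemolysed, clotted or lost samples, and the SAP has a separate unscheduled-visit listing (16.2.9.8). A follow-up sample logged as unscheduled might leave the scheduled value in place. This stands as a limit on certainty: the rule can overwrite the value, and it is not established that it always will. But the footnote has no exception, and Protocol 8.5 allows the same extra blood for safety assessments.

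Third, the last repeat need not be normal, because repeats may also stop at baseline or at loss of clinical significance. That stands.

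Fourth, the same footnote under 14.3.9 has little bearing, since urine and serology are tested only at screening. That stands too.

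Fifth, laboratory values are not a listed endpoint, and 14.3.8 is split by sequence rather than by product, so it cannot compare test with reference whichever value is used. This limits the consequence without removing the bias.

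**Conclusion.** The concern holds for SAP Table 14.3.8 at post-dose visits. As worded, the latest-result rule combined with Protocol 8.3.4 can replace an abnormal value with a less abnormal one, in one direction, and so remove the size of a liver-enzyme rise from the only quantitative laboratory summary. In the illustration, one participant moves a sequence mean by 1.7 to 10.6 U/L and the maximum from between 100 and 410 down to 42. The ALT values are assumptions; no observed rate or size of elevation is available.

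The conclusion rests on reading the footnote's repeats as including clinical follow-up samples, which its wording allows and nothing in the SAP excludes. It does not extend to a claim that every such value is overwritten, that the replacement is always normal, or that the event itself goes unreported. The bioequivalence conclusion is not affected. The point is worth correcting before database lock, because a choice between first and repeat values made after seeing them would be hard to defend.

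**What to change.** Replace the repeat sentence in the footnote to Table 14.3.8 with wording to this effect: for post-dose visits the first valid scheduled result is summarised; a repeat replaces it only if the first sample was technically invalid (haemolysed, clotted or lost); repeats taken for clinical follow-up are listed as unscheduled. The latest-result rule may stay for screening.

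A row giving the worst post-dose value for ALT, AST and total bilirubin is optional. Across periods it would mix the two products, so it would describe magnitude and would not compare them.

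The cost is minor shell wording and programming. The repeat sample status field already in Listing 16.2.8.2 should help. No new data, visit or procedure is needed. The downside is a less clean-looking table.

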14.3.9 Summary of qualitative safety laboratory variables (Safety set)

Lambda Therapeutic Research Ltd.

Confidential

Table 14.3.9

Summary of qualitative safety laboratory variables (Safety set)

Parameters (Unit)	Visit	Result	Statistics	TRTR (N=xx)	RTRT (N=xx)	Total (N=xx)
HBsAg	Screening	XXX	n (%)	xx (xx.x)	xx (xx.x)	xx (xx.x
		XXX	n (%)	xx (xx.x)	xx (xx.x)	xx (xx.x
		XXX	n (%)	xx (xx.x)	xx (xx.x)	xx (xx.x
	Assessment Visit X	XXX	n (%)	xx (xx.x)	xx (xx.x)	xx (xx.x
		XXX	n (%)	xx (xx.x)	xx (xx.x)	xx (xx.x
		XXX	n (%)	xx (xx.x)	xx (xx.x)	xx (xx.x
	Assessment Visit Y	xxx	n (%)	xx (xx.x)	xx (xx.x)	xx (xx.x
		XXX	n (%)	xx (xx.x)	xx (xx.x)	xx (xx.x
		XXX	n (%)	xx (xx.x)	xx (xx.x)	xx (xx.x
Etc.	Etc.					

N = Number of subjects in safety set, n = Number of subjects in respective categories Note: Percentages are calculated based on the total number of subjects in each category.

Treatment specification \rightarrow T = Test Product and R = Reference Product.

In case of repeat sample collection latest result has been considered for the analysis.

Reference Listing: 16.2.8.1

Output Generated on: DDMMMYYYY hh:mm

<Note to Programmer: This table will continue for all other Laboratory parameters and some additional test.>

14.3.10 Summary of concomitant medication (Safety set)

Lambda Therapeutic Research Ltd.

Confidential

Project No. 0110-23

Table 14.3.10

Summary of concomitant medication (Safety set)

	TRTR	RTRT	Total
	(N=xx) n (%)	(N=xx) n (%)	(N=xx) n (%)
At least one concomitant medication	xx (xx.x)	xx (xx.x)	xx (xx.x)
Medication 1	xx (xx.x)	xx (xx.x)	xx (xx.x)
Medication 2	xx (xx.x)	xx (xx.x)	xx (xx.x)
Medication 3	xx (xx.x)	xx (xx.x)	xx (xx.x)
Etc.	xx (xx.x)	xx (xx.x)	xx (xx.x)

N = Number of subjects in safety set, n = Number of subjects in respective categories Note: Percentages are calculated based on the total number of subjects in each category. Treatment specification \rightarrow T = Test Product and R = Reference Product. Reference Listing: 16.2.10

In-text tables

Table 1: Summary of Adverse events

Adverse events (as per MedDRA PT - Version xxx)	Albendazole tablets IP 400 mg Test (T)	Albendazole 400 mg tablets Reference (R)	Total
XXXXXXXX	X	X	х
XXXXXXXX	X	X	X
XXXXXXXX	X	X	X
XXXXXXXX	X	X	X
XXXXXXXX	X	X	X
XXXXXXXX	X	X	X
XXXXXXXX	X	X	X
XXXXXXXX	X	X	X
XXXXXXXX	X	X	X
XXXXXXXX	X	X	X
XXXXXXXX	X	X	X
otal	X	X	X

Table 2: Summary of Adverse Events with System Organ Class

System Organ Class	MedDRA (PT) (Version xxx)	Albendazole tablets IP 400 mg Test (T)	Albendazole 400 mg tablets Reference (R)	No. of events
XXXXXXXXX	XXXXXXXX	X	X	X
XXXXXXXX	XXXXXXXX	X	X	X
XXXXXXXX	XXXXXXXX	X	X	X
XXXXXXXX	XXXXXXXX	X	X	x
XXXXXXXX	XXXXXXXX	X	X	X
XXXXXXXX	XXXXXXXX	X	X	x
XXXXXXXXX	XXXXXXXX	X	X	x
XXXXXXXX	XXXXXXXX	X	X	x
XXXXXXXX	XXXXXXXX	X	X	X
XXXXXXXX	XXXXXXXX	X	X	x
XXXXXXXX	XXXXXXXX	X	X	x
Total		X	X	X

Listings

16.2.1 Subject disposition

16.2.1.1 Screen failure subjects

16.2.1.1 Scre	en failure	subjects					
Screening No.	Date of screening	Subject Study Completion Status	Reason for Screen Failure	'Withd	'Physician decision' rawal by subject', please specify	,	
Screening No.	Date screer	of inclusion/e	-fulfillment of xclusion criteria or lation, please specify		Death', Date of Death	_	
6.2.1.2 Stud	dy completi		Date of Completion or		of last dose of study	y Reason	for
Subject			decision', 'Withdrawa's event', specify	l If Non-	fulfilment of inclusi	- ,	If 'Death', Date of Death
6.2.1.3 Sub	ject distri	bution in analysis po	pulation				
Subject no.	Sequenc	ce Subjects include Randomized s			Subjects included in PK set		
6.2.1.4 Inc	lusion - Ex	clusion criteria					
Subject se		pes the subject meet l inclusion criteria?	If No, Mark the IN criterion number(s)		Does the subject meany exclusion criter	•	Mark the EXCLUSI

16.2.1.5 I	inclusion c	riteria d	lescription					
Со	de	Ir	nclusion criteri	la descriptio	on			
16.2.1.6 E	Exclusion c	riteria d	lescription					
Со	de	Εz	clusion criteri	la descriptio	on			
16.2.2 Pro	tocol devia	ations						
Subject no.	Sequence	Visit No.	Date of deviati Occurrence	ion Protoc Sectio				
Subject no.	Sequence	Visit No.	Type (Major/Minor)	Reason for deviation	Description of the Deviation	Corrective Action	Preventive Action	Impact Assessment
	•	•	available data from the analysis	the source.>				
16.2.3.1 S	Subjects exc	cluded fr	om the analysis	(PK set)				
Subject	No.	Period	Reason					
								

16.2.4 Demographic data

16.2.4.1 Demographic data and baseline characteristics

Screening Subject no. no. Sequence Sequence Sequence Sequence (Screening) Date of Informed consent form consent form signed signed (Study Specific)	Date of Age Birth (Years)	Gender	Ethnicity	Race	If Other, please specify
--	------------------------------	--------	-----------	------	--------------------------------

< Note for programmers: This listing will be created on Randomized set.>

16.2.4.2 Personal history

Subject	Sequence	Personal history assessment	Reproductive
no.	sequence	done for female subject?	status

16.2.4.3 Medical and surgical history details

Subject no.	Sequence	Visit	Nature of condition	Medical/Surgical history term	Medical/Surgical history code

Subject no.	Sequence	Visit	Start date	End date	Ongoing	

16.2.4.4 Physical examination

Subject no.	Sequence	Visit	Date of assessment	Body System	Result	Specify if Abnormal CS/Not Done	Any New clinically significant abnormality finding or worsening of condition since last assessment?

Subject no.	Sequence	Visit	If yes, please select body System	If yes, please specify abnormality

16.2.4.5	Medication	history
----------	------------	---------

Subject no.	Sequence	Subject taken any medication from 14 days prior to dosing of period I?

16.2.5 Compliance and drug concentration data

16.2.5.1 Study drug administration

Subject no.	Sequence	Visit	Study drug administration performed?	Date of study drug administration	Time of Study drug administration	Mouth check done after dosing?	If 'No', then specify	Any deviation during dosing?	If 'Yes', please specify
-------------	----------	-------	--	-----------------------------------	---	--------------------------------------	-----------------------------	------------------------------	--------------------------------

